^e Tetanus immunization to take place any time after leukapheresis and prior to day 1

^f Where chemistry labs indicated, the following serum tests are to be performed: Chem 7 (sodium, potassium, bicarbonate, BUN, creatinine, glucose), ALT, AST, bilirubin, alkaline phosphatase, amylase, TSH (thyroid stimulating hormone), and LDH

^g Procedures can be +/- 7 days of this visit; scans to be done prior to biopsy (and study treatment for Arm 2)

^h Can be +/- 7 days of this visit

ⁱ Can be +/- 7 days of this visit, and not required if this is off-study visit and previous scans already confirmed disease progression

^j CT of chest at this time point only as clinically indicated

^k PT/INR only required for those subjects who will be undergoing a biopsy. May be performed up to 30 days prior to biopsy, required same day if subject is on coumadin^l If NaF PET/CT is available as standard of care procedure, this may be substituted for bone scan (bone scintigraphy), however all pre-treatment and post-treatment tests must use the same modality (NaF PET/CT or bone scintigraphy)

^m See section 9 for whether or not biopsy and FLT PET is required.

Plan of Treatment: ARM 3 – EXTENDED TREATMENT COHORT

Vaccine / Treatment Visit:	SCREENING		Day 1	Week 3 (21 +/- 3 days from Day 1)	Week 6 (21 +/- 3 days from week 3)	Week 9 (21 +/- 3 days from week 6)	Week 12 (21 +/- 3 days from week 9)	Week 15 (21 +/- 3 days from week 12)	Week 18 (21 +/- 3 days from week 15)	Week 21 (21 +/- 3 days from week 18)	Week 24 (21 +/- 3 days from week 21)	Week 27 (21 +/- 3 days from week 24)	Week 30 (21 +/- 3 days from week 27)	Week 33 (21 +/- 3 days from week 30)	Week 36 (21 +/- 3 days from week 33)	Week 39 (21 +/- 3 days from week 36)	Week 42 (21 +/- 3 days from week 39)	Week 45 (21 +/- 3 days from week 42)	END OF STUDY Week 48 (21 +/- 3 days after week 45)	28-Day Follow Up (28 +/- 7 days after off-treatment visit)
	Within 6 wks of day 1	Within 4 wks of day 1																		
History and Physical Exam																				
History	X																			
Consent	X																			
Physical Exam, ECOG PS		X	X		X		X		X		X		X		X		X		X	X
Tox assessment ^a		X	X	X	X	X	X	X	X	X	X	X	X	X	X	X	X	X	X	X
Lab Tests																				
CBC	X		X	X ⁱ	X ⁱ	X ⁱ	X ⁱ	X ⁱ	X ⁱ	X ⁱ	X ⁱ	X ⁱ	X ⁱ	X ⁱ	X ⁱ	X ⁱ	X ⁱ	X ⁱ	X ⁱ	X
Chemistry panel ^f	X		X	X ⁱ	X ⁱ	X ⁱ	X ⁱ	X ⁱ	X ⁱ	X ⁱ	X ⁱ	X ⁱ	X ⁱ	X ⁱ	X ⁱ	X ⁱ	X ⁱ	X ⁱ	X ⁱ	X
PT/INR		X ^k					X ^k													
Serum testosterone	X																			

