PSA and PAP	X		X	X ⁱ	X ⁱ	X ⁱ	X ⁱ	X ⁱ	X ⁱ	X ⁱ	X ⁱ	X ⁱ	X ⁱ	X ⁱ	X ⁱ	X ⁱ	X ⁱ	X ⁱ	X ⁱ	X
Procedures																				
CT chest/abdomen/pelvis	X						X ^g				X ^h				X ^h					X ^h
Bone scan	X						X ^g				X ^h				X ^h					X ^h
Leukapheresis		X ^b									X ^{bh}									
FLT PET scan ^m		X ^c					X ^g													
NaF PET/CT scan ^m		X			X ^g		X ^g													
Tissue biopsy ^m		X ^d					X ^g													
Tetanus immunization		X ^e																		
Blood for immune analyses		X			X		X				X				X					X (X) ⁿ
Blood for CTC analysis		X			X		X				X				X					X (X) ⁿ
Treatments																				
DNA immunization			X	X	X	X	X	X	X	X	X	X	X	X	X	X	X	X		
Pembrolizumab infusion			X	X	X	X	X	X	X	X	X	X	X	X	X	X	X	X		

^a Study coordinator or research nurse review of systems

^b For patients unable to undergo leukapheresis, a 200-mL blood draw (green top tubes) may be performed instead

^c FLT PET scan – within 4 weeks (28 days) of day 1 – to provide baseline study for comparison prior to treatment

^d Biopsy within 2 weeks prior to day 1

^e Tetanus immunization to take place any time after leukapheresis and prior to day 1

^f Where chemistry labs indicated, the following serum tests are to be performed: Chem 7 (sodium, potassium, bicarbonate, BUN, creatinine, glucose), ALT, AST, bilirubin, alkaline phosphatase, amylase, TSH (thyroid stimulating hormone), and LDH

^g Procedures can be +/- 7 days of this visit; scans to be done prior to biopsy

^h Can be +/- 7 days of this visit

ⁱ Blood draws can be up to 3 days prior to this visit

^j CT of chest at this time point only as clinically indicated

^k PT/INR only required for those subjects who will be undergoing a biopsy. May be performed up to 30 days prior to biopsy, required same day if subject is on coumadin

^m See section 9 for whether or not biopsy, FLT, or NaF PET is required.

ⁿ Blood collected for immune analysis only if not collected within previous 60 days

Plan of Treatment: ARM 4 – EXTENDED TREATMENT COHORT

Vaccine / Treatment Visit	Screening																													

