Hepatitis (including liver-associated pain and/or elevation of serum liver function tests) occurred in 2 (0.5%) of 411 melanoma patients receiving pembrolizumab, including 1 patient with a grade 4 event. The time to development of symptoms was 22 days. Patients will be monitored by laboratory tests for changes in liver function. Pembrolizumab will be held for grade 2 or higher liver function test abnormalities, and permanently discontinued for grade 3 or 4 events. Patients with grade 2 or higher events will be treated with high-dose systemic corticosteroids (≥ 40 mg prednisone or equivalent per day) for at least one week followed by taper, or as clinically indicated. If retreatment is possible, treatment with pembrolizumab will continue to be held until the toxicity resolves to < grade 2.

Immune-mediated hypophysitis adverse events:

Hypophysitis occurred in 2 (0.5%) of 411 melanoma patients receiving pembrolizumab, including 1 patient with grade 2 and 1 patient with grade 4 events. The median time to development of symptoms was 1.5 months. Patients will be monitored for signs and symptoms of hypophysitis, which could include headache, visual disturbances, polyuria, and polydipsia; lab tests will be performed as clinically indicated. Pembrolizumab will be held for grade 2 or higher hypophysitis, and permanently discontinued for grade 4 events. Patients with grade 2 or higher events will be treated with high-dose systemic corticosteroids (≥ 40 mg prednisone or equivalent per day) for at least one week followed by taper, or as clinically indicated. If retreatment is possible, treatment with pembrolizumab will continue to be held until the toxicity resolves to < grade 2.

Immune-mediated nephritis adverse events:

Nephritis occurred in 3 (0.7%) of 411 melanoma patients receiving pembrolizumab, including 1 patient each with grade 2, 3, or 4 events. Two of these patients developed acute interstitial nephritis. The time to development of symptoms was 11 months, and 5 months after the last dose in at least one patient. Patients will be monitored for changes in renal function, with other lab tests as clinically indicated. Pembrolizumab will be held for grade 2 or higher nephritis, and permanently discontinued for grade 3 or higher events. Patients with grade 2 or higher events will

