1. Subjects will receive pTVG-HP DNA immunizations intradermally on the deltoid area of the lateral arm (preferentially left arm) with 0.25 mL administered at each of two adjacent sites.
 2. Following vaccinations, the subjects will be observed for 60 minutes for unanticipated adverse events.
- M. 3-Month Follow-up - Day 85 (14 +/- 3 days after day 71 visit)
1. Physical examination, symptoms assessment, and ECOG performance score.
 2. Blood draw for CBC, chemistry panel, serum PSA and PAP (can be performed +/- 7 days of this visit)
 3. 10 ml peripheral blood (red-top tubes) for sera to evaluate antibody responses, and 100 ml peripheral blood (green-top heparinized tubes) for T-cell response evaluation and CTC analysis (can be performed +/- 7 days of this visit)
 4. CT scan of abdomen and pelvis, bone scintigraphy (can be performed +/- 7 days of this visit, but prior to pembrolizumab treatment for patients in Arm 2)
 5. FLT PET/CT scan (can be performed +/- 7 days of this visit, but prior to pembrolizumab treatment for patients in Arm 2)
 6. Tissue biopsy of same metastatic lesion as in pre-treatment period (can be performed +/- 7 days of this visit, but prior to pembrolizumab treatment for patients in Arm 2)

ARM 2 SUBJECTS ONLY – Anti-PD-1 #1:

7. Pembrolizumab 2 mg/kg administered intravenously over 30 minutes
8. Subjects will be observed for an additional 30 minutes for unanticipated adverse events. Vital signs (temperature, heart rate and blood pressure) will be assessed and recorded by the staff prior to, and at the end of, the treatment period.

N. DAY 106 – (21 +/- 3 days after day 85 visit):

1. Physical examination, symptoms assessment, and ECOG performance score.
2. Blood draw for CBC, chemistry panel, serum PSA and PAP

ARM 2 SUBJECTS ONLY – Anti-PD-1 #2:

3. Pembrolizumab 2 mg/kg administered intravenously over 30 minutes
4. Subjects will be observed for an additional 30 minutes for unanticipated adverse events. Vital signs (temperature, heart rate and blood pressure) will be assessed and recorded by the staff prior to, and at the end of, the treatment period.

O. DAY 127 – (21 +/- 3 days after day 106 visit):

1. Physical examination, symptoms assessment, and ECOG performance score.
2. Blood draw for CBC, chemistry panel, serum PSA and PAP

ARM 2 SUBJECTS ONLY – Anti-PD-1 #3:

3. Pembrolizumab 2 mg/kg administered intravenously over 30 minutes

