8. Tissue biopsy – metastatic site – to take place within 2 weeks prior to day 1 (minimum of 6 patients per cohort)

W. Immunization #1 (Day 1)

1. Physical examination, symptoms assessment, and ECOG performance score
2. Blood draw for CBC, differential and platelets, chemistry panel, PSA and PAP
3. Subjects will receive pTVG-HP DNA immunizations intradermally on the deltoid area of the lateral arm (preferentially left arm) with 0.25 mL administered at each of two adjacent sites.
3. Following vaccinations, the subjects will be observed for 60 minutes for unanticipated adverse events.
4. Pembrolizumab 2 mg/kg, maximum 200 mg dose, administered intravenously over 30 minutes
5. Subjects will be observed for additional 30 minutes for unanticipated adverse events.

- X. Immunization #2 - Week 3 (21 +/- 3 days after Day 1 visit)
Immunization #4 - Week 9 (21 +/- 3 days after Week 6 visit)
Immunization #6 - Week 15 (21 +/- 3 days after Week 12 visit)
Immunization #8 - Week 21 (21 +/- 3 days after Week 18 visit)
Immunization #10 - Week 27 (21 +/- 3 days after Week 24 visit)
Immunization #12 - Week 33 (21 +/- 3 days after Week 30 visit)
Immunization #14 - Week 39 (21 +/- 3 days after Week 36 visit)
Immunization #16 - Week 45 (21 +/- 3 days after Week 42 visit)

1. Symptoms assessment
2. Blood draw for CBC, differential and platelets, and chemistry panel (can be performed +/- 3 days of this visit).
3. Blood draw for PSA and PAP (can be performed +/- 3 days of this visit)
4. Subjects will receive pTVG-HP DNA immunizations intradermally on the deltoid area of the lateral arm (preferentially left arm) with 0.25 mL administered at each of two adjacent sites.
5. Following vaccinations, the subjects will be observed for 60 minutes for unanticipated adverse events.
6. Pembrolizumab 2 mg/kg, maximum 200 mg dose, administered intravenously over 30 minutes
7. Subjects will be observed for additional 30 minutes for unanticipated adverse events.

- Y. Immunization #3 – Week 6 (21 +/- 3 days after Week 3 visit)

8. Physical examination, symptoms assessment, and ECOG performance score
9. Blood draw for CBC, differential and platelets, chemistry panel, PSA and PAP
10. 10 ml peripheral blood (red-top tubes) for sera to evaluate antibody responses, and 100 ml peripheral blood (green-top heparinized tubes) for T-cell response evaluation and CTC analysis (can be performed +/- 7 days of this visit)

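### Section 9.X and the Arm 3 calendar disagree on whether safety labs may follow the pembrolizumab dose at 8 of 16 visits; Arm 2 Day 85 has a smaller, related gap

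*Combined protocol and SAP*

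**What the plan says.** **Arm 3.** Section 9.X covers weeks 3, 9, 15, 21, 27, 33, 39 and 45. Its item 2 reads "Blood draw for CBC, differential and platelets, and chemistry panel (can be performed +/- 3 days of this visit", and item 3 gives PSA and PAP the same window. Each of these visits includes a pembrolizumab infusion. Footnote i of the Arm 3 calendar, attached to the CBC, chemistry and PSA/PAP cells from week 3 to week 48, reads "Blood draws can be up to 3 days prior to this visit". Sections 9.Z, AA, BB and CC use the footnote's window for weeks 12, 18, 24, 30, 36 and 42.

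**Arm 2.** Section 9.M (Day 85) includes a block headed "ARM 2 SUBJECTS ONLY – Anti-PD-1 #1". Item M.2 reads "Blood draw for CBC, chemistry panel, serum PSA and PAP (can be performed +/- 7 days of this visit", and M.3 gives the immune and CTC blood the same window. Items M.4 to M.6 (CT and bone scan, FLT PET, biopsy) have that window too, but add "but prior to pembrolizumab treatment for patients in Arm 2". Footnote g of the Arm 2 calendar, attached to the Day 85 lab and immune-blood cells, reads "Procedures can be +/- 7 days of this visit; scans to be done prior to biopsy (and study treatment for Arm 2".

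**Use of the labs.** Section 8 on hepatitis states "Pembrolizumab will be held for grade 2 or higher liver function test abnormalities, and permanently discontinued for grade 3 or 4 events". The nephritis and thyroid paragraphs likewise rely on monitoring of renal and thyroid function. Section 7.B.4 uses the 3-month PSA as a second baseline for PSA response and progression.

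**The concern.** A laboratory value can inform the decision to give or hold a dose only if the blood is drawn before that dose. In Arm 3, two parts of the plan give different answers for the same visits, and staff working from Section 9.X could dose first and draw afterwards while following the text. Section 9.X lists a symptoms assessment but no physical examination, so the labs are the main objective check at those visits.

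In Arm 2, Section 9.M orders three procedures relative to the first pembrolizumab dose and leaves the blood draws unordered. Chiefly this affects the data. A Day 85 PSA or immune sample drawn after the infusion is no longer a pre-pembrolizumab value, yet the PSA serves as a baseline. Secondary objective 2 compares concurrent with delayed pembrolizumab on T-cell responses and PD-1 expression, so the timing of the immune sample also matters to its interpretation.

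**Working it through.** The plan states no figure on this point. The check is a count of visits and a comparison of windows.

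**Arm 3: dosing visits by lab window.** Section 6 allows at most 16 pembrolizumab doses, at Day 1 and every 3 weeks to week 45.

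| Visits | Section 9 window | Calendar window | Doses |
|---|---|---|---|
| Day 1 (9.W) | none stated | none stated | 1 |
| Week 6 (9.Y) | none stated | up to 3 days before | 1 |
| Weeks 3, 9, 15, 21, 27, 33, 39, 45 (9.X) | 3 days either side | up to 3 days before | 8 |
| Weeks 12, 18, 24, 30, 36, 42 (9.Z, AA, BB, CC) | up to 3 days before | up to 3 days before | 6 |

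1 + 1 + 8 + 6 = 16, which matches the planned maximum. The conflict covers 8/16 = 50% of doses (8/15 = 53% if Day 1 is left out).

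If the labs at a 9.X visit are drawn after the dose, the latest scheduled results come from the preceding visit, 21 +/- 3 days earlier, so 18 to 24 days. For the week 3 dose (Day 1 + 21 = Day 22 nominally), those are the Day 1 labs.

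**Arm 2: Day 85.** The Arm 2 doses fall on Days 85, 106, 127 and 148. Sections 9.N to 9.P list the labs on the last three days with no window, so 1 of 4 doses is affected. The latest permitted draw is nominally Day 85 + 7 = Day 92.

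The scheduled chemistry before Day 85 is on Day 43. Nominal gap: 85 - 43 = 42 days. Days 43 to 57, 57 to 71 and 71 to 85 are three intervals of 14 +/- 3 days, so the gap runs from 3 x 11 = 33 to 3 x 17 = 51 days.

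**Side by side.** The Arm 3 passages contradict each other. The Arm 2 passages do not: M.2, M.3 and footnote g agree that blood may be drawn up to 7 days after the visit. What they lack is the ordering relative to the dose that M.4 to M.6 contain.

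**The case against.** The best reply has four parts.

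- **The Arm 3 calendar already excludes a post-dose draw, and one subsection is out of line.** True, but that does not settle which text governs. Section 9 describes the calendar as a summary of itself, and neither states an order of precedence.

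- **The windows permit a late draw but do not require one.** This stands and limits the severity. In addition, Sections 8 and 9 contain no sentence requiring results to be seen before dosing. Agreeing one draw window would therefore not by itself show that results inform the dose.

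- **Arm 2 Day 85 is the first pembrolizumab dose.** A reader might infer that earlier pembrolizumab toxicity could be missed there. None can exist yet, although Section 8's general hold rule also covers vaccine-related events. A reader might also infer that no usable safety baseline would exist. However, Sections 11.F.4.1 and 14.A.1 plan chemistries at 6- to 12-week intervals, and 42 days (at most 51) does not exceed 12 weeks. Symptom assessments are also scheduled on Days 57, 71 and 85.

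- **The Day 85 immune sample is not designated a vaccine-only read-out.** This stands. Section 10.B puts the primary immune analysis at 6 months, and Section 11.F.5.2 names no Day 85 comparison.

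The 22-day time to hepatitis symptoms in Section 8 might also be set against the week 3 dose. It rests on 2 of 411 melanoma patients and carries little weight.

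**Conclusion.** The point holds at moderate severity. The main part is the Arm 3 contradiction: at 8 of 16 planned doses, Section 9.X permits labs used by the Section 8 hold rules to be drawn up to 3 days after the dose, while the calendar and the neighbouring visit sections do not. The documents do not support saying that the plan as a whole allows this in Arm 3.

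The Arm 2 part is secondary. It affects 1 of 4 doses, with draws up to 7 days afterwards. What is at stake is an older chemistry result and a PSA or immune sample that may follow anti-PD-1 exposure. The documents give no basis for estimating how far a few days of exposure would shift either measure, or how many draws were in fact late.

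The counts assume the full dosing schedule and the visit windows as written. Sections 2.F and 6.A close Arms 1 and 2 once Arm 3 opens, and 11 Arm 3 patients had been treated by January 2018, so few or no Arm 2 Day 85 visits are likely to remain. Arm 4's stated lab windows run only to 3 days before the visit, so it does not share the problem.

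**What to change.** The sponsor should:

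1. Reconcile Section 9.X items 2 and 3 with Arm 3 footnote i and the other Arm 3 visit sections, so that one lab window applies, and state whether the draw must precede pembrolizumab.
2. Reconcile Section 9.M items 2 and 3 and Arm 2 footnote g with items 4 to 6, and state the same for the labs, PSA and immune/CTC blood.
3. For samples already collected, flag Arm 2 Day 85 PSA and immune samples drawn after the dose in any analysis that treats Day 85 as a baseline or as a pre-pembrolizumab time point.

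Which window is right is for the sponsor to decide; no dose, hold threshold or clinical rule is proposed here. The cost is a few lines of wording and a check of draw times against infusion times. No draws are added; scheduling tightens slightly if the narrower window is adopted.
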